2.6 Handling of Missing Data

The primary and secondary analyses have been designed to characterize the risk of various events for the time period each subject has his or her first on study catheter. In this framework, missing data will exist if a subject discontinues follow-up for these events while the study is ongoing and the initial catheter is still in place. The statistical technique that will be used in the primary statistical analysis to deal with missing data is to treat the subject as censored at the time the catheter is removed for reasons other than CRBSI or follow-up is prematurely discontinued. This method will be appropriate if the reason for discontinuing follow-up is not related to a change in the subject that would be predictive of an increased risk of a CRBSI.

To explore the reasons for missing data and to assess any bias associated with premature discontinuation, all reasons for subjects terminating study follow-up will be summarized by treatment arm.

A sensitivity analysis will be performed in which cases considered to be indeterminate by the Clinical Adjudication Committee are treated as CRBSI events.

2.7 Safety Analyses

Statistical analyses will be descriptive in nature and testing for statistical significance will not be routinely applied. Safety analyses will be based upon the clinical database only. Events recorded in the safety database will be reconciled with the clinical database prior to database lock.

2.8 Interim Analysis

A DSMB will meet periodically to review the accumulating study data. The primary purpose of these reviews is to monitor safety and data quality.

Additionally, the DSMB will oversee interim analyses for efficacy and for futility that will be performed when 28 CAC-adjudicated CRBSI events (1/2 of the required total number of 56 events) have occurred. If statistical significance is obtained for the primary efficacy endpoint at this time, the recommendation will be to stop the study early for efficacy. If the futility analysis indicates that continuing the study would be futile, the recommendation will be to stop the study early for futility. In either case, the DSMB will report its recommendation only to the CorMedix Executive Committee, which will make the final decision as to whether or not to stop the study in consultation with the FDA.

3 Summary Tables Listings and Figures

3.1 General Conventions

Unless otherwise stated, summary statistics including the number of subjects (n), mean, standard deviation, median, minimum and maximum will be presented for continuous variables. Minimum and maximum values will be presented to the same decimal precision as the raw values, the mean and median

values to one more, and the standard deviation, to two more decimal places than the raw values. For categorical variables, per category, the absolute counts (n) and percentages (%) of subjects with data, and if appropriate, the number of subjects with missing data, will be presented. Percentages will be presented to one decimal place.

For efficacy and safety analyses, age will be calculated relative to the date of randomization.

For adverse events reported on a per-subject basis, medical history and concomitant medications, the denominator for the percentage calculation will be the number of subjects in the analysis population and in the subgroup of interest at risk in each treatment arm.

All p-values will be rounded to 4 decimal places. If a p-value is less than 0.0001 it will be displayed as “< 0.0001”.

All non-efficacy summary tables will use either the Randomized Population or the Safety Population. All efficacy summary tables will use the Full Analysis Population unless specified otherwise. Summaries will be provided by treatment group.

Not all data collected (e.g., vital signs at each dialysis visit) will be summarized or listed. All such data will be included in the appropriate analysis file for display and summarization as needed during the preparation of the clinical study report (i.e., ad hoc displays).

3.2 Subject Disposition and Treatment

The total number of subjects screened, randomized, completed, discontinued from the study, and in each analysis population will be summarized by treatment group and overall. The reason for termination for all subjects who discontinued will be summarized by treatment group and overall. A listing of subjects who discontinued from the study by reason for termination will also be presented.

Subjects randomized but not included in a given analysis population will be summarized by analysis population and the reason for exclusion will be presented.

3.3 Violations of Inclusion/Exclusion Criteria

Subjects enrolled in the trial without meeting the inclusion/exclusion criteria will be summarized for the Randomized Population with the following information: treatment assigned and inclusion/exclusion criteria violated.

3.4 Study Treatment

The following information will be presented by treatment arm and overall:

- duration of exposure
- total number of times drug administered
- total number of vials administered
- average dose
- compliance (100*No. of dialysis sessions at study site at which the correct dosing was administered/total number of dialysis sessions at study site)

- dose interruptions: percentage of months with dose interruptions and percentage of months with more than 3 consecutive missed doses.

3.5 Demographics and Baseline Characteristics

Descriptive summaries of demographic and baseline characteristics will be presented by treatment group and overall for the Randomized Population. No statistical testing will be performed. Baseline characteristics will include summaries of the following:

- Subject demographics including age, sex, and race
- Baseline disease characteristics
- Pre-existing medical conditions
- Prior therapies

3.5.1 Medical History

Medical history will be descriptively summarized based upon the MedDRA system organ class (SOC) and preferred term by treatment and overall for the Safety Population. Data summaries will be sorted by the overall frequency of reporting within SOC.

3.6 Clinical Data

3.6.1 Concomitant Medications

Concomitant medications will be descriptively summarized based upon the coded values (WHO) by treatment for the Safety Population. Data summaries will be sorted by the overall frequency of recorded use. Medications with end dates prior to dosing will not be included in these summaries. A table of medications used prior to dosing (including routine medications given with HD) will also be provided.

3.7 Analysis of Efficacy Endpoints

3.7.1 CRBSI

The clinical criteria associated with CRBSI will be summarized by treatment group. This summary will consist of the number and percent of subjects with each of the following

- Fever (defined as $\geq 37.8^{\circ}$ C)
- Rigors, defined as shivering from a feeling of being cold, often with copious sweating, as documented by a medical professional
- Tachycardia, defined as a heart rate greater than 100 beats per minute
- Tachypnea, defined as a RR greater than 24 breaths per minute
- Low blood pressure, defined as a systolic blood pressure less than 90, as measured by a clinician (RN or MD) with a BP cuff, or a decrease in blood pressure greater than 30 mmHg
- An obvious change in mental status from previously documented baseline

A listing of this information will also be provided.

3.7.2 Primary Efficacy Analysis

The number of subjects in each treatment arm will be summarized in the Full Analysis Population using the following categories:

- Occurrence of CAC-adjudicated CRBSI,
- Subject followed without occurrence of CAC-adjudicated CRBSI at the time the study was closed to further follow-up, or
- Subject was censored (provide count for each reason censored) for other reasons.

The p-value for the log-rank comparison, hazard ratio (HR) with 95% confidence interval (active/control), and the incidence of CRBSI with 95% CI for each treatment group will be presented. The log-rank test will be performed using PROC LIFETEST in SAS. The HR and confidence interval will be calculated using PROC PHREG in SAS with only treatment in the MODEL statement and study day as the response variable.

Kaplan-Meier curves will be displayed by treatment group for the time until CRBSI (implemented using PROC LIFETEST).

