5.3 STUDY COMPLETION, EARLY WITHDRAWAL, NEW CATHETER PLACEMENT

5.3.1 Study Completion

A subject is considered as completing the study if at least one of the following conditions is met:

- All assessments through study closure;
- CRBSI meeting primary endpoint definition;
- Catheter removal;

- Death;
- Transfer to a non-study site; or
- Termination of dialysis.

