2.4 Statistical Assessment of the Trial Objectives

2.4.1 Primary Endpoint Analysis

The primary analysis will be conducted using a log-rank test for the time to CRBSI at an overall 2-sided 5% alpha level. The null hypothesis is that there is no difference in the hazard rates of CRBSI over time between the two treatments. The time until CRBSI will be calculated as the number of days post randomization until the occurrence of a CAC-adjudicated CRBSI or the subject is censored. Subjects without a CRBSI will be treated as censored in this analysis if the catheter is removed for reasons other than CRBSI (e.g., catheter removed because no longer required) or follow-up is completed in the absence of CRBSI. Because an interim analysis for efficacy will be performed, the method of Pocock will be used to control the overall alpha level. Therefore, the nominal significance level at the interim and final statistical analyses for the primary efficacy endpoint will be 0.0294.

The primary analysis will be based upon the Full Analysis Population. While testing will be based upon the log-rank test, the estimated treatment effect will be the difference between treatment groups in the incidence rate of CRBSI, calculated as the number of subjects with a CRBSI divided by the number of catheter-days of follow-up over subjects (follow-up will be based upon the same time as used for the log-rank test). The rates will be presented as the event rates per 1000 catheter-days with a 95% confidence interval for the purpose of comparison of rates between the treatments. This confidence interval will be derived assuming that the number of catheter-days until CRBSI follows an exponential distribution.

In the primary analysis of the primary endpoint, cases considered to be indeterminate by the CAC will be excluded. A sensitivity analysis will be performed in which cases considered to be indeterminate will be treated as CRBSI events.

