1.1 Efficacy Analyses

Primary Endpoint

The primary endpoint is catheter-related blood stream infection (CRBSI), defined as one positive blood culture (other than for coagulase negative *Staphylococcus*, which requires a confirmatory culture) from:

1. a peripheral site or blood line sample or
2. either the arterial or venous catheter hub (or the venous or arterial dialysis circuit blood lines if on dialysis)

in a patient with no other apparent source of bloodstream infection other than the hemodialysis catheter, as assessed by the Clinical Adjudication Committee (CAC).

The primary analysis of the primary endpoint was performed at the interim analysis, and it resulted in a positive outcome and the stopping of the study. This analysis of this endpoint represents the final formal analysis for this endpoint. Nevertheless, in order to summarize all of the available information on this endpoint, the analysis of the primary endpoint will be repeated using all of the data through the LPLV. The p-value from this analysis will be reported to provide a measure of the strength of evidence of efficacy from the study but it will not represent a second test of the null hypothesis for this endpoint. As for the interim analysis, the analysis of the primary endpoint based on all of the data through the LPLV will be conducted based on the Full Analysis Population using the Kaplan-Meier method. The time until CRBSI will be calculated as the number of days post randomization until the occurrence of a CAC-adjudicated CRBSI. A patient will be considered to have a CRBSI event if there is a CAC-determined CRBSI. If there is no such CRBSI, the patient will be censored at the earliest of the following dates:

1. Date of catheter removal, if any
2. Date of study completion, if any
3. Date of last study drug dose plus 3 days

Three days was added to the date of last study drug dose because the study drug would be withdrawn at the next dialysis session, which would typically be about three days later.

In this analysis of the primary endpoint, cases adjudicated as indeterminate by the CAC will not be considered to be CRBSI cases. A sensitivity analysis will be performed in which cases adjudicated as

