indeterminate will be considered to be CRBSI cases. Subgroup analyses of the primary analysis of the primary endpoint will be conducted as described in the Statistical Analysis Plan. These analyses will be performed based (1) on all of the efficacy data through the data cutoff date for the interim analysis and also (2) on all of the efficacy data through the LPLV.

Secondary Endpoints

The secondary endpoints are as follows:

- Catheter Removal: Defined as catheter removal for any reason during the follow-up period of the trial.
- Loss of Catheter Patency: Defined as required use of a tissue plasminogen activating factor (tPA) or removal of the catheter because of dysfunction during the follow-up period of the trial.

Analyses of these endpoints were conducted and provided to the Data Safety Monitoring Board at the time of the interim analysis. Unlike the primary endpoint, however, the primary analyses of these endpoints will be based on data through the LPLV.

Time until catheter removal for any reason and time to loss of catheter patency will be analyzed based on the Full Analysis Population using the Kaplan-Meier method as for the primary endpoint.

A patient will be considered to have had loss of catheter patency if either of the following conditions are met:

1. If the reason for study completion is specified as “Catheter Removal (not due to CRBSI)” and the reason (for catheter removal) is indicated as being “Catheter Malfunction/Dysfunction – Loss of patency” or
2. If the Reported Name of Drug Med or Therapy (Preferred) is “Alteplase” and the item “For tPA usage, if the usage was directly related to a loss of patency” is indicated as “Yes”.

The time of the event will be the number of days between randomization and the event. (If both of the above conditions are met, the date of occurrence of the earlier condition will be used.) If there is no such loss of catheter patency, the patient will be censored at the earliest of the following dates:

1. Date of catheter removal, if any
2. Date of study completion, if any
3. Date of last study drug dose plus 3 days

A patient will be considered to have had a catheter removal if there is a date of catheter removal. If a patient does not have a date of catheter removal, the patient will be considered censored at the earliest of the following dates:

1. Date of study completion, if any
2. Date of last study drug dose plus 3 days

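### The Kaplan-Meier CRBSI curves censor catheter removal and death, so any absolute risk read from them is hypothetical and too high; add cumulative incidence curves

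*SAP*

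**What the plan says.** **Display.** SAP 3.7.2 plans that "Kaplan-Meier curves will be displayed by treatment group for the time until CRBSI". Addendum 1.1 says that the repeat analysis of the primary endpoint "will be conducted based on the Full Analysis Population using the Kaplan-Meier method", and that the two secondary endpoints are analysed "using the Kaplan-Meier method as for the primary endpoint". The addendum names a method, not a particular figure. Neither document mentions cumulative incidence or competing risks.

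**Censoring.** SAP 2.4.1 states: "Subjects without a CRBSI will be treated as censored in this analysis if the catheter is removed for reasons other than CRBSI", or if "follow-up is completed in the absence of CRBSI". Addendum 1.1 censors at the earliest of catheter removal, study completion and last dose plus 3 days. Neither rule names death. It enters through protocol 5.3.1, where "A subject is considered as completing the study if at least one of the following conditions is met" introduces a list that includes both catheter removal and death.

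**Aim and effect measure.** SAP 2.6 says that the primary and secondary analyses are designed to "characterize the risk of various events for the time period each subject has his or her first on study catheter". It defends censoring on the ground that the reason for stopping follow-up does not predict a higher CRBSI risk. SAP 2.4.1 makes the difference in CRBSI rates per 1,000 catheter-days the estimated treatment effect. SAP 3.7.2 adds the hazard ratio and counts of subjects by reason for censoring.

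**The concern.** Once the study catheter is out or the subject has died, a CRBSI on that catheter cannot occur. Kaplan-Meier treats such a subject like one whose follow-up merely stopped, as if still able to have the event later. One minus Kaplan-Meier therefore answers a hypothetical question: how many subjects would have a CRBSI by a given day if every catheter stayed in and nobody died.

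The independence argument in SAP 2.6 addresses a different problem. Even if removal and death are wholly unrelated to CRBSI risk, they still prevent the event, and the curve still overstates how often it happens.

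Competing events matter in this population. Catheter removal is a secondary endpoint, entry requires an expected catheter need of only 60 days, and some subjects are expected to be treated for 2 years or more. At the planned 56 events in about 900 subjects, 1 − 56/900 = 94% would leave observation without a CRBSI. Some of those are still followed at study closure, so this is not a removal rate.

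The curve is the only planned display of CRBSI risk building up over time, and readers commonly take absolute risks and numbers needed to treat from such figures.

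**Working it through.** **1. The plan's own figure.** The documents state no absolute CRBSI risk to reproduce. The related design figure is 56 events for 80% power at a hazard ratio of 0.45, two-sided 5% alpha and two Pocock looks. With the Schoenfeld approximation and a two-look Pocock boundary (critical value 2.178, nominal level 0.0294 as stated), 80% power needs 54.7 events, and 56 events give 81.0%. This rests on the cause-specific comparison, so the present point does not touch it.

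**2. Inputs for the curves.**
- Hazard ratio 0.45: SAP 1.5 (55% reduction).
- Control CRBSI hazard *l*: assumed. Protocol 2.1 gives 2 to 5.5 per 1,000 catheter-days as background, not as a design rate. I use 1.0 and 2.0 in the table, and 0.5 to 2.0 or 5.5 in ranges.
- Removal plus death hazard *m*: assumed, as the documents give none. It is constant and equal in both arms unless stated.

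**3. Formulas (constant hazards).**
- Kaplan-Meier risk with removal and death censored: 1 − exp(−*l t*)
- Actual cumulative incidence: *l*/(*l*+*m*) × [1 − exp(−(*l*+*m*)*t*)]

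The first exceeds the second whenever *m* is above zero.

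**4. Example, control arm: *l* = 1.0 and *m* = 5 per 1,000 days.**
- Day 60: 1 − exp(−0.06) = 5.8%, against (1/6) × [1 − exp(−0.36)] = 5.0%.
- Day 365: 1 − exp(−0.365) = 30.6%, against (1/6) × [1 − exp(−2.19)] = 14.8%.

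For Neutrolin, *l* = 0.45 per 1,000 days. At day 365 this gives 1 − exp(−0.16425) = 15.1%, against (0.45/5.45) × [1 − exp(−1.98925)] = 7.1%.

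| Assumed *l* (control), *m* | Day | Control: KM v actual | Arm difference in points: KM v actual |
|---|---|---|---|
| 1.0 and 5 per 1,000 days | 60 | 5.8% v 5.0% | 3.2 v 2.7 |
| 1.0 and 5 per 1,000 days | 90 | 8.6% v 7.0% | 4.6 v 3.8 |
| 1.0 and 5 per 1,000 days | 365 | 30.6% v 14.8% | 15.4 v 7.7 |
| 2.0 per 1,000 days, mean 180 days to removal or death | 180 | 30.2% v 19.7% | 15.3 v 10.1 |
| 2.0 per 1,000 days, mean 180 days to removal or death | 365 | 51.8% v 24.8% | 23.8 v 12.2 |

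Differences are taken before rounding. A difference of 15.4 points is a number needed to treat of about 6.5; 7.7 points is about 13.

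**5. Ranges.**
- Day 365, *l* from 0.5 to 2.0 and *m* from 2 to 8 per 1,000 days: Kaplan-Meier control risk is 1.35 to 2.97 times the actual risk.
- Day 180, mean time to removal or death from 60 to 730 days: at *l* = 2.0 per 1,000, Kaplan-Meier stays at 30.2% while the actual risk runs from 10.3% to 27.0%. At 0.5 per 1,000 it is 8.6% against 2.8% to 7.6%; at 5.5 per 1,000 it is 62.8% against 24.4% to 56.8%.

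**6. Unequal removal.** In the example of step 4, let Neutrolin have *m* = 4 instead of 5 per 1,000 days. Its actual one-year risk becomes (0.45/4.45) × [1 − exp(−1.62425)] = 8.1%, and the difference falls to 14.8 − 8.1 = 6.7 points. The Kaplan-Meier difference stays at 15.4.

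**7. Check by simulation.** With 400,000 subjects per arm, *l* = 2.0 per 1,000 days for control and a mean of 180 days to removal or death, the day-365 estimates are 51.8% (Kaplan-Meier) against 24.8% (Aalen-Johansen) for control, and 27.8% against 12.6% for Neutrolin. The rates come back at 2.00 and 0.90 per 1,000 catheter-days, so they are not distorted.

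**The case against.** The strongest reply is that the plan never relies on the curve for absolute benefit. Its absolute measure is the rate difference per 1,000 catheter-days, which handles removal and death properly. No Kaplan-Meier risk at a fixed time, risk difference or number needed to treat is planned. This stands, and it rules out the stronger reading that the trial's main statement of absolute benefit is inflated.

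A reader might also infer that the curve contradicts a stated estimand, because SAP 2.6 speaks of risk while the first study catheter is in place. That phrase sits in the missing-data section and can equally mean a rate per catheter-day, which the plan estimates correctly. On that reading the fault is confined to the figure.

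Further points carry weight. SAP 3.7.2 already counts subjects with CRBSI and by reason for censoring, and catheter removal is analysed in its own right, so competing removal will be visible. The one-year figures use a late horizon: in the example of step 4 only exp(−2.19) = 11% of control subjects would still be at risk at day 365, and the gap at day 60 is small. For patency, removal for dysfunction is itself an event, so fewer removals compete, and SAP 3.7.3 names no patency curve.

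None of this makes the curve an estimate of actual risk. The planned counts show how many subjects had a CRBSI but not by when.

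**Conclusion.** The point holds as one about display. Each arm's cumulative risk read from the planned Kaplan-Meier curves exceeds the actual risk over the life of the study catheter. The direction is certain given any removal or death. The arm difference is also too large in every scenario computed here. The size cannot be derived from the documents: it rests on assumed constant hazards, and ranges from under one percentage point at day 60 to about a doubling at one year in the 1.0 and 5 per 1,000 example.

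It would be wrong to infer that the log-rank test, the hazard ratio, the rate difference, the 56 events, the power or the decision to stop at the interim analysis is affected. All use cause-specific quantities, for which this censoring is appropriate under the independence that SAP 2.6 assumes. That death is censored is an inference from protocol 5.3.1, not an explicit SAP rule. The same logic applies to any loss-of-patency curve, but the CRBSI magnitudes do not carry over. This is a worthwhile, inexpensive improvement, not a flaw in the primary analysis.

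**What to change.** In SAP 3.7.2 and Addendum 1.1:

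- Add Aalen-Johansen cumulative incidence curves of CRBSI by arm, with catheter removal for reasons other than CRBSI and death as competing events and study closure as censoring.
- Take any quoted absolute risk, difference or number needed to treat from these curves.
- Label any Kaplan-Meier plot as the hypothetical risk with no removal and no death.
- Name death explicitly in the event and censoring rules. State how the addendum's last-dose-plus-3-days date is treated when it falls before a recorded removal or death.
- For any loss-of-patency curve do the same, with removal for reasons other than dysfunction and death as competing events.

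Keep the log-rank test, hazard ratio and rate difference as planned. The removal and completion dates and the reasons for censoring are already used in the plan, and the method is standard. The cost is one extra figure (a second if patency is plotted) and absolute figures that look less favourable.
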